**Protocol** 

IRAS ID: 346681

REC Ref:

Volume Reduction Therapy

#### 2. LAY SUMMARY

One of the treatments to improve symptoms and life expectancy in patients with severe COPD is lung volume reduction therapy. Due to the high risks associated with surgical techniques, one-way expiratory endobronchial valves have been developed to reduce lung volume and these are inserted into the targeted airway(s) via bronchoscopy. When the airway supplying the targeted lung (which is typically severely damaged and working) is blocked with the valve(s), the targeted lung will deflate resulting in lung volume reduction. For this to work, the target lung should only have air flow coming from the main airway supplying it and no abnormal connection with other parts of the lung ("collateral ventilation"). Collateral ventilation would prevent the lung from deflating despite treatment.

Current practice to assess collateral ventilation is using a software to analyse CT images of the lungs and a bronchoscopy technique called Chartis to measure air flow in the airways. When collateral ventilation has been excluded following Chartis assessment, suitable patients could be offered valve treatment. However, these assessments are not perfect. This can result in either suitable patients not offered treatment due to technical limitations, or patients selected for treatment who do not benefit. Therefore, it is important to find other techniques that could improve the current assessment methods for better patient selection for treatment.

We believe that MRI scanning with a special gas (hyperpolarised xenon) breathed in during the scan could potentially identify patients for treatment. The xenon gas is harmless in the quantity we use. This technique shows the movement of xenon within the lungs and moving out of the lungs into the bloodstream, similar to how oxygen is absorbed. In COPD patients, we have found that xenon MRI scans has the potential to detect collateral ventilation.

We aim to study whether these patterns of collateral ventilation will predict the success of lung volume reduction therapy using endobronchial valves. We will study the pattern of collateral ventilation in those who have been directly selected to undergo valve treatment (Cohort A) and those who have been deemed not eligible for valve treatment (Cohort B). By doing so, we may be able to establish a pattern on xenon MRI that will help select those who are more likely to benefit

Protocol

REC Ref:

from valve treatment. The success of valve treatment is also dependent on the blood flow to the targeted lung

Our overall aim is to further our understanding into the factors such as air and blood flows that could affect the success rate of valve treatment. We also wish to evaluate the value of xenon MRI as a non-invasive method in the assessment of patients being considered for valve treatment. Learning the nature and pattern of these air flows through xenon MRI may help better select patients for valve treatment and include patients who would have been excluded through conventional assessments.

### 3. SYNOPSIS

In this study, we aim to identify and characterise the pattern of ventilation in 2 groups of patients with COPD using hyperpolarised xenon-129 MRI (HPX-MRI): A) patients who have been selected and subsequently undergone lung volume reduction therapy using endobronchial valves (EBV), B) those who have been identified as not eligible for endobronchial lung volume reduction therapy using current selection criteria. We also aim to assess and describe the physiological changes following endobronchial lung volume reduction therapy.

Study Title	Hyp E rpolarised X enon P u L monary MR I in the Evaluation for Endobron C hial Lung Volume Reduct I on T herapy (EXPLICIT)			
Internal ref. no. / short title	EXPLICIT			
Study registration	This study will be re	gistered on the ISRCTN		
Sponsor	Oxford University Hospitals NHS Foundation Trust [name] . Email: [contact]			
Funder	Medical Research Cou	uncil (MRC)		
Study Design	Feasibility/pilot			
Study Participants	Up to 40 patients			
Sample Size	Cohort A – up to 20 patients Cohort B – up to 20 patients			
Planned Study Period	Up to 24 months			
Planned Recruitment period	Aug 2025 – Feb 2027			
	Objectives Outcome Measures Timepoint(s)			
Primary	To characterise the pattern of ventilation on HPX-MRI in those with confirmed CV	Quantitative and/or qualitative detection of differences in the pattern of ventilation in the two cohorts being investigated:	Baseline and follow-up	

Protocol

IRAS ID: 346681 REC Ref:

HypErpolarised Xenon PuLmonary MRI in the Evaluation for EndobronChial Lung

**Volume Reduction Therapy** 

	and those treated with EBV	,	Those with and without confirmed CV; Those who were and weren't successfully treated with EBV.	
Secondary	To describe the physiological changes of the lungs seen on HPX-MRI post-EBV treatment	a)	Quantitative and/or qualitative differences of HPX-MRI findings pre- and post-EBV therapy	Baseline and follow-up
Intervention(s)	Not applicable			
Comparator	Not applicable			_

### 4. ABBREVIATIONS

6MWD	6-minute walk distance
6MWT	6-minute walk test
BD	Bronchodilator
CAT	COPD Assessment Test
CRF	Case report form
СТ	Computed tomography
CV	Collateral ventilation
COPD	Chronic obstructive pulmonary disease
DALYs	Disability-adjusted life years
DV	Delayed ventilation
EBV	Endobronchial valves
FC	Fissure completeness
FDA	Food and Drug Administration
FEV 1	Forced expiratory volume in 1 second
FVC	Forced vital capacity
GOLD	Global Initiative for Chronic Obstructive Lung Disease
HPX-MRI	Hyperpolarised  Xe MRI
HRCT	High resolution computed tomography
LH	Lung hyperinflation
LVR	Lung volume reduction
LVRS	Lung volume reduction surgery

Protocol

IRAS ID: 346681

REC Ref:

HypErpolarised Xenon PuLmonary MRI in the Evaluation for EndobronChial Lung Volume Reduction Therapy

mMRC	Modified Medical Research Council
MRI	Magnetic resonance imaging
PFTs	Pulmonary function tests
QCT	Quantitative CT
RV	Residual volume
SAE	Serious adverse event
SGRQ	St. George's Respiratory Questionnaire
TLC	Total lung capacity
TLVR	Total lung volume reduction
U.S.	United States
VDP	Ventilation defect percentage
V/Q	Ventilation/perfusion

#### 5. BACKGROUND AND RATIONALE

Chronic obstructive pulmonary disease (COPD) has been defined as "a heterogeneous lung condition characterized by chronic respiratory symptoms (dyspnoea, cough, expectoration) due to persistent abnormalities of the airways (bronchitis, bronchiolitis), and/or alveoli (emphysema), that often results in progressive airflow limitation." With more than 3 million deaths annually, COPD is the third leading cause of global mortality and the seventh leading cause of global poor health. COPD was the cause of 2.6% of global disability-adjusted life years (DALYs) in 2015. In the UK, there were 1.26 million patients with COPD in 2021 with an overall annual cost of £2 billion spent on acute treatment of exacerbations and chronic management of the condition. Of note, the annual cost is projected to increase to £2.6 billion and the cumulative total costs over 20 years are expected to exceed £46 billion with the bulk of the costs spent on patients with mild and moderate disease.

Chronic inflammation in COPD results in structural damage of small airways and alveolar tissue leading to airway narrowing and chronic expiratory flow obstruction, increased mucous production and decreased lung elasticity. Consequently, static lung hyperinflation (LH) occurs when there is increased lung volumes following parenchymal destruction and loss of elastic recoil. Dynamic hyperinflation is distinct from static LH in which there is incomplete lung emptying due to airway obstruction which is then interrupted by the next inspiration leading to further air trapping. Both static LH and further dynamic hyperinflation during exercise contributes to excessive loading to respiratory muscles resulting in functional weakness in respiration reducing exercise tolerance. This vicious cycle of overloading and hyperinflation contributes to the neuromechanical dissociation of the respiratory system, one of the many factors causing the symptom of dyspnoea (or breathlessness) in COPD.

Dyspnoea is the most frequently experienced symptom and is the major determinant of physical and mental health status in COPD. Identification and management of LH is consequently

Protocol IRAS ID: 346681
HypErpolarised Xenon PuLmonary MRI in the Evaluation for EndobronChial Lung REC Ref:

Volume Reduction Therapy CI: [name]

important in improving symptoms, exercise tolerance and quality of life. Furthermore, treatment of LH has extrapulmonary benefits and impedes disease progression, rate of exacerbations and mortality. LH has been found to exert negative effects on cardiovascular function by reducing the heart size and left ventricular diastolic function. LH is also a risk factor for recurrent infective exacerbations and is a predictor of mortality in COPD. Pharmacological treatments such as inhaled bronchodilators and non-pharmacological strategies such as pulmonary rehabilitation have been extensively studied and reported to be effective in improving lung volumes.

It has been shown that the mechanical reduction of lung volumes by eliminating the severely emphysematous parts of the lungs improves the dynamics of ventilation-to-perfusion matching and lung elastic recoil. Surgical methods of mechanical reduction include lung volume reduction surgery (LVRS) and bullectomy.  LVRS is unsuitable for high-risk patients because of its greater morbidity and mortality in these patients and can only be offered to highly selected patients.  As a result, non-surgical options of lung volume reduction (LVR) have been explored such as the bronchoscopic deployment of one-way expiratory endobronchial valves (EBV), airway bypass stents and coils, all of which aim to reduce LH.

Bronchoscopic deployment of EBV is the most extensively studied endobronchial LVR technique. The only two U.S. FDA-approved one-way valves currently in clinical use are the Zephyr (duckbillshaped) and Spiration (umbrella-shaped) valve systems. A meta-analysis of all eligible clinical trials investigating the benefits of these two valve systems have found significant improvement in FEV1 (an objective measure of airway obstruction), lung residual volume (RV, an objective measure of lung hyperinflation), 6-minute walk distance (6MWD, an objective measure of exercise capacity) and St. George's Respiratory Questionnaire (SGRQ, a patient-reported measure of quality of life) for at least 6 months when compared with standard medical treatment. 17 The largest multi-centre randomised controlled trial with 190 participants and the longest follow-up period of 12 months to date is the LIBERATE study using the Zephyr valve system. The mean difference between groups in LIBERATE at 12-month follow-up for post-bronchodilator (post-BD) FEV1 in percent change was +17.96%, RV -522 mL, 6MWD +39.31m, SGRQ score -7.05 (lower score indicating better health) and modified Medical Research Council Dyspnoea scale -0.8 points (mMRC, lower score indicating less breathlessness).18 Sustained benefits have been seen in FEV1, RV and 6MWD even after 3 years. 19 Pneumothorax, haemoptysis and post-procedural pneumonia were the most common complications, usually occurring within 6 months of EBV treatment. Endobronchial LVR treatment has also been reported to be an independent positive predictor of survival and reduces the number of COPD exacerbations.

The greatest benefit of EBV therapy in terms of FEV1 improvement is seen in those with heterogenous emphysematous disease and complete lobar fissure seen on quantitative CT (QCT) analysis. Incomplete lobar fissure is associated with interlobar collateral ventilation (CV) which may prevent EBV treatment from working. CV is the passage of air between alveoli through channels outside of the normal airways. Interlobar CV is more prevalent in COPD possibly due to the formation of new channels between lobes as a consequence of lung parenchymal destruction. The presence of interlobar CV allows movement of air from an untreated lobe to the EBV-targeted lobe, subsequently preventing collapse and volume reduction.

IRAS ID: 346681

**REC Ref:** 

To identify potential CV which would cause EBV treatment to fail, interlobar fissure completeness (FC) using QCT analysis and bronchoscopic assessment using a catheter-based system called Chartis is performed prior to treatment.  Chartis is performed using a catheter with an inflatable balloon at the distal tip to occlude the main lobar airway. This is connected to a console that measures airflow, pressure and resistance across the catheter.26 Once the target bronchus is occluded, absence of flow after 5 minutes signifies the absence of CV. Chartis has a proven 75 -90% accuracy prediction rate in EBV-treatment response when it determines there is no CV. 27-29 QCT analysis utilises specific automated software to measure FC based on high resolution CT (HRCT) images. The Chartis system is recommended in those with partial FC (80 – 95%) to bolster the confidence of CV assessment but is optional in those with >95% of FC and EBVtreatment is not advocated in those with incomplete fissures (<80%). 24,31

When treated with EBV, approximately 50% of patients achieved the target of ≥15% post-BD FEV₁ increase, 84% achieved the target total lung volume reduction (TLVR) of ≥350mL and 48% achieved the target mMRC dyspnoea score improvement. As not all patients with confirmed negative CV will benefit from the EBV therapy, it is important to ensure that patients are carefully selected for the procedure. Table 1 summarises the current recommendations for patient selection.

Table 1 – Current recommendations for suitability of EBV therapy 			
Criterion	Details		
Symptom limitation	mMRC ≥ 2, 6MWD between 100 – 500m.		
Residual volume >175% predicted and RV/TLC >55%	Thresholds set in line with previous trials.		
Post-BD FEV1 of 15 - 50% of predicted	Thresholds set in line with previous trials.		
No evidence of significant coexistent pulmonary pathology on HRCT	Reversible pathologies should be treated pre-EBV treatment. Exclude in severe bronchiectasis and pulmonary fibrosis. High risk of pneumothorax if bulla present in or adjacent to the target lobe.		
Heterogeneity of disease	Perfusion scan recommended in homogenous disease to target the lobe with low perfusion for EBV treatment.		
Absence of CV in the EBV-targeted lobe	QCT measurement for FC +/- Chartis system.		
Prior surgery	Exclude if prior surgery in ipsilateral lung		
Hypercapnia	Exclude unless stable on NIV treatment for at least 3 months		
Clinically stable disease	Exclude if >3 COPD exacerbations requiring hospitalisation despite optimal medical management in the past 12 months		
Suitability for sedation or general anaesthesia and bronchoscopy	Exclude in untreated significant cardiovascular diseases or high risk of complications from general anaesthesia		

Protocol

HypErpolarised Xenon PuLmonary MRI in the Evaluation for EndobronChial Lung Volume Reduction Therapy

CI: [name]

Smoking cessation	To eliminate a contributing factor to disease		
	progression		
Undergone pulmonary rehabilitation and receiving guideline pharmacologic therapy	To optimise medical treatment prior to invasive therapy		
Severe congestive heart failure (left ventricular ejection fraction <40%) or pulmonary hypertension (right ventricular systolic pressure >50 mmHg)	Exclude due to poor outcomes		

Unfortunately, the modalities currently used to assess CV may fail. FC measurements can be under- or overestimated between software used in QCT analysis. The Chartis system may also fail in about 20% of cases. Failure has been attributed to low patient tolerance during bronchoscopy, inaccurate position or inadequate inflation of the balloon, the presence of secretions and false negative measurements.

Because of its 20% failure rate, plus the need for bronchoscopy, a technique that reduces the failure rate and removes the need for bronchoscopy would clearly be of benefit. Hyperpolarised xenon-129 (Xe) is a state-of-the-art, non-invasive, ionising-radiation-free functional imaging modality that is reproducible, quantitative, safe and well-tolerated which involves minimal patient effort. The inhalation of Xe gas imaged using MRI (HPX-MRI) enables direct visualisation of lung structure as it flows and fills the airways and alveoli, mirroring the passage of atmospheric gases. Abnormalities in ventilation, due to airway narrowing or bullae formation for example, can be qualitatively and quantitatively measured. The process of the pro

Proof of principle for the ability of hyperpolarised gas MRI to directly visualise CV was first described by Marshall *et al.* Using a static imaging technique of a single breath-hold of up to 20 seconds, they were able to demonstrate delayed filling of ventilation defects thought to be due to collateral ventilation in four out of 10 COPD patients scanned. Delayed ventilation (DV) could be attributed to other factors such as air trapping and significant peripheral airway obstruction. However, in their cohort of patients, collateral ventilation was more plausible due to the peripheral to central pattern of delayed filling of ventilation defects. Chen *et al.* was able to assess DV using dynamic HPX-MRI in 13 out of 15 COPD scanned and suggested further research to establish dynamic HPX-MRI ability to assess CV.

The aim of this study would be to assess the movement of Xe gas in the lungs using HPX-MRI to determine whether in patients with severe COPD it can reliably detect and measure collateral ventilation.

### 6. OBJECTIVES AND OUTCOME MEASURES

	Objectives	Outcome Measures	Timepoints
Primary	ventilation on HPX-MRI in	Quantitative and/or qualitative detection of differences in the pattern of ventilation in the two cohorts being investigated:	

Protocol IRAS ID: 346681
HypErpolarised Xenon PuLmonary MRI in the Evaluation for EndobronChial Lung REC Ref:

Volume Reduction Therapy

		a) Those with and without	
		confirmed CV;	
		b) Those who were and weren't successfully treated with EBV.	
Secondary	To describe the physiological changes of the lungs seen on HPX-MRI post-EBV treatment	Quantitative and/or qualitative differences of HPX-MRI findings pre- and post-EBV therapy	Baseline and follow-up

#### 7. STUDY DESIGN

This is a prospective, observational, cohort study comprising two patient cohorts – Cohort A – COPD patients, patients selected and planned for EBV treatment and Cohort B – COPD patients deemed unsuitable for EBV treatment due to presence of CV determined by the current gold standard assessments. The comparison of patterns of ventilation and/or physiological movement of gas using HPX-MRI will allow the assessment of collateral ventilation in the two cohorts of patients.

The study will recruit patients into the two cohorts through the local hospital-based COPD clinics. Participants who have been worked up for EBV therapy and their cases discussed at the local COPD multi-disciplinary team (MDT) meeting will be identified by the Clinician and informed of the study. COPD MDT comprises of respiratory physician(s), thoracic surgeon(s), thoracic radiologist(s), specialist nurse(s), respiratory physiotherapist(s) and occupational therapist(s).

The research team may participate in the MDT meetings where possible and may highlight potential patients suitable for the study to the clinicians. The clinicians involved in the MDT and the patients clinical care will inform the potential patients of the study and, if they agree, will provide them with the PIS and consent form, and ask their permission to be contacted by the research team to further discuss the study. If they agree to be contacted, a member of the research team will contact them, explain the study, assess eligibility and complete the informed consent form with the patient if they wish to participate. They will then invite them to undertake their baseline study visit locally at the Churchill Hospital, Oxford University Hospitals NHS Foundation Trust.

At the baseline visit, participants written consent (unless obtained prior to baseline visit), demographics, past medical history, alcohol and smoking history are collected, where possible. They may have their baseline heart rate, blood pressure, respiratory rate and oxygen saturations recorded. These and all trial data will be recorded in the EXPLICIT eCRF. As part of their clinical work-up for EBV therapy, a thin section volumetric CT chest (and its corresponding QCT analysis using StratX software) +/- Chartis assessment, full pulmonary function tests (PFTs), 6-minute walk test (6MWT), mMRC dyspnoea score and SGRQ should have been completed, where possible. If any of these (except PFTs, StratX and Chartis) were not completed as a part of their clinical

assessment before their baseline visit, they shall be carried out during their baseline visit, where possible.

HPX-MRI chest and/or perfusion MRI may be performed at the baseline visit. In the event of a new respiratory condition developed since the clinical CT chest as part of the EBV work-up before the baseline visit, a research low-dose CT may be performed to ensure the lung parenchyma has not changed. This will be justified by a research clinician, e.g. in the event of a new chest infection.

Following their baseline visit, participants who have had undergone EBV therapy may be invited to complete one additional follow-up visit after their first clinical post-procedure follow-up. This follow-up visit should happen at 6 months of their clinical follow-up. All the assessments carried out as part of their EBV clinical work-up (except StratX and Chartis) should have been repeated during their clinical follow-up. If any of these were not completed as part of their clinical assessment before their follow-up visit, they shall be carried out during their follow-up visit, where possible. HPX-MRI Chest and/or perfusion MRI may be repeated as part of their follow-up visit.

Participants who have not undergone EBV treatment will be invited at 6 months following their baseline visit to repeat all the assessments carried out during their baseline visit (except StratX and Chartis), where possible. HPX-MRI Chest and/or perfusion MRI may be repeated as part of their follow-up visit. In the event of a new respiratory condition developed since their baseline visit, a research low-dose CT may be performed to ensure the lung parenchyma has not changed. This will be justified by a research clinician, e.g. in the event of a new chest infection.

Each visit may comprise of one or more appointments to complete all the necessary assessments for the study. The research team will endeavour to coincide the research visits with pre-arranged clinical appointments at the hospital to reduce the burden of travel to the hospital site. Participants may be reimbursed up to £50 per visit if they have had to travel to the hospital site specifically for this research study.

[figure not shown]
All information will be recorded in a locally approved, secure, study database.

#### 8. PARTICIPANT IDENTIFICATION

#### 8.1. Study Participants

Study participants will be recruited to one of the cohorts as explained in the diagram below.

Protocol
HypErpolar
Volume Re
CI: [name]

Figure 1 – EXPLICIT recruitment and study assessments flow chart.

Abbreviations: 6MWT – 6-minute walk test, CAT – COPD assessment test, CT – Computed tomography, CV – Collateral ventilation, EBV – Endobronchial valve, FCS – Fissure completeness score, HPX-MRI – Hyperpolarised xenon magnetic resonance imaging, mMRC – Modified Medical Research Council, PFTs – Pulmonary function tests, QCT – Quantitative CT, SGRQ – St. George's Respiratory Questionnaire

### Cohort A (No evidence of CV and planned for EBV treatment)

- Data from this cohort will provide information on the patterns of ventilation when no CV has been established using QCT and/or Chartis assessment.
- Subgroup analysis will help identify if there are differences in the patterns of ventilation in those with confirmed successful treatment with EBV (radiologically confirmed atelectasis, and/or lung function and/or symptomatic improvement) and those who are deemed to not have successful treatment with EBV.
- Subgroup analysis will help identify if there were differences in the patterns of ventilation in those who have CV ruled out using QCT assessment only and those who have CV ruled out using both QCT and Chartis assessments.

Cohort B (Ineligible for EBV treatment following current gold standard assessments)

 Data from this cohort will provide information on the patterns of ventilation when CV has been established using current standard assessments and those deemed ineligible for EBV treatment due to inconclusive or incomplete Chartis assessment.

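### EBV success is an any-of rule with no threshold or timing, so primary contrast (b) will probably have few failures and is partly circular on follow-up scans

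*Protocol*

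**What the plan says.** The only definition of successful EBV treatment in the protocol is in Section 8.1, under Cohort A: "radiologically confirmed atelectasis, and/or lung function and/or symptomatic improvement". It gives no size of improvement, no named measure, no time of assessment and no rule for combining components beyond the and/or.

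Sections 3 and 6 place this label in the primary outcome as contrast (b): "Those who were and weren't successfully treated with EBV". Section 3 gives the timepoints of the primary outcome as "Baseline and follow-up". Section 8.1 describes the same comparison as a subgroup analysis within Cohort A. Section 11.2 uses the label again when it relates DV to treatment success. Section 11.1 says that no separate SAP is in use, so this text is the operative definition.

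Section 5 gives three response rates after valve treatment from the cited trial. For lung volume it reports that "84% achieved the target total lung volume reduction (TLVR) of ≥350mL". The rate is about 50% for the FEV1 target (a rise of at least 15% after bronchodilator) and 48% for the mMRC target. Section 5 separately gives 75–90% as the accuracy of a Chartis no-CV finding in predicting treatment response. Section 11.3 plans 20 patients in Cohort A and does not consider how many treatment failures to expect.

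**The concern.** There are two problems.

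First, an any-of rule can only make success more common than its most common component. Leaving out thresholds cannot lower the rate and would be expected to raise it. With 20 treated patients, the failure group may be too small to say much about its ventilation pattern. Because no measure or time is fixed and the study is unblinded (Section 9.5), the label could also be settled after the scans have been seen.

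Second, the lay summary (Section 2) asks whether ventilation patterns predict the success of treatment. Only a scan taken before treatment can answer that. On a follow-up scan, a lobe that was called a success because it collapsed will be poorly ventilated for that reason alone. Part of any success-versus-failure difference at follow-up is then built into the definition.

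**Working it through.** **Cohort A size (Section 11.3).** The inputs are 20–30 EBV procedures a year, 50–60% uptake and 18 months. 20 × 0.60 = 12 and 30 × 0.50 = 15 a year, which matches the stated 12–15. Over 1.5 years that is 18 to 22.5. The midpoint is 25 × 0.55 × 1.5 = 20.6, so the planned 20 is reproduced. Crossing the extremes gives 15 to 27.

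**Success rate under an any-of rule.** For component rates p_i, the composite rate is max(p_i) if the responses are fully nested and 1 − Π(1 − p_i) if they are independent. It cannot exceed min(1, Σp_i). Expected failures are 20 × (1 − rate). The rates are those of Section 5 and are assumed to carry over to this centre.

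| Components counted | Nested | Independent | Upper bound |
|---|---|---|---|
| FEV1 50%, TLVR 84%, mMRC 48% | 84%: 3.2 failures | 1 − 0.50 × 0.16 × 0.52 = 95.8%: 0.8 | 100%: 0 |
| FEV1 50%, mMRC 48% | 50%: 10 failures | 1 − 0.50 × 0.52 = 74%: 5.2 | 98%: 0.4 |

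The first row assumes that TLVR counts as a component. Section 8.1 does not name it. It could fit under lung function, since Section 9.6.3 lists RV and TLC among the pulmonary function tests.

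If the 75–90% Chartis figure is read as a success rate, expected failures are 20 × 0.25 = 5 down to 20 × 0.10 = 2.

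**Spread around these expectations (binomial, n = 20).**
- At 95.8% success, the chance of no failure is 0.9584^20 = 43%, and of at most one failure 80%.
- At 84%, the chance of no failure is 3% and of at most three 60%. The central 80% range is 1 to 5.
- At 74%, the central 80% range is 3 to 8.

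**Precision.** Take the clearest possible pattern, DV in all k failures. The lower limit of the exact 95% interval is 0.025^(1/k): 29% for k = 3, 48% for k = 5 and 69% for k = 10. With one failure it is 2.5%, which is no information.

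As an illustration with inputs not in the protocol, assume DV in 80% of failures and 20% of successes, and a two-sided Fisher test at 0.05. Power is about 1%, 17% and 50% with 1, 2 and 3 failures, and 62–64% with 5 or 10.

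**Circularity.** Side by side, Section 8.1 lets atelectasis alone define success, and Section 3 lists follow-up as a timepoint for comparing ventilation by success. For patients classified through atelectasis, label and outcome then describe the same collapsed lobe. For patients classified only through lung function or symptoms the link is not built in. On baseline scans it is absent for everyone.

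**The case against.** The strongest reply is that this is a declared exploratory pilot. Section 11.3 makes no power claim and Section 11.2 aims largely to describe, so a few failures can still be described. That stands as far as power goes: no stated calculation is wrong. It does not excuse a primary grouping that two readers could apply differently.

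A reader might infer that the protocol's own rates put success at 84% or more. They do not. The 84% is for TLVR, which Section 8.1 does not name, and partial volume loss is not atelectasis. Missing thresholds push the rate up, but the documents do not say by how much.

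A reader might also infer that contrast (b) is empty. That fits only 0 or 1 failures, near the independence end, and responses within one patient are unlikely to be independent. At 3 to 5 failures the contrast is imprecise but can be described.

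Nor is contrast (b) circular as a whole. The timepoint entry covers the entire primary row, success can only be established at follow-up, follow-up MRI is optional (Section 7), and nothing states that follow-up scans will be offered as evidence of prediction. The problem is that the text allows it.

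Untreated Cohort B patients do not enlarge the failure group, because Section 11.2 lists them separately.

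Finally, one might choose the FEV1 target because it splits patients about 10 to 10. With 50% FEV1 non-response and 16% TLVR non-response, at least 50 − 16 = 34 of every 50 FEV1 non-responders (68%) met the volume target. Section 5 says CV acts by preventing collapse and volume reduction, so that split would dilute the signal under study.

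**Conclusion.** The point holds in this form. Success is an any-of label without threshold or timing, and it defines half of the primary outcome. In 20 treated patients the expected number of failures is about 3 to 1 if TLVR counts, 5 to 2 on the Chartis figure, and 10 to 5 if only the FEV1 and mMRC targets count. These are nested-to-independent ranges, not full bounds, and they assume that the Section 5 rates transfer and that the quoted thresholds apply. The literal rule has no thresholds and would be expected to give fewer failures.

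Contrast (b) is therefore likely to be very imprecise, though not necessarily empty. On follow-up scans it is partly true by construction where success means atelectasis. At baseline it is not.

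**What to change.** 1. State in Sections 3, 6 and 11.2 that contrasts (a) and (b) use the baseline HPX-MRI only, and that follow-up scans serve the secondary objective.
2. In Section 11.2, make the main analysis of DV and treatment effect the relation of baseline DV to continuous 6-month change in RV and FEV1. RV is the hyperinflation measure closest to the CV mechanism. Both are already among the study's lung function tests.
3. If a success/failure label is kept, replace the any-of rule in Section 8.1 with one pre-specified criterion with a threshold and an assessment time. Choose it for its link to the CV mechanism (lobar collapse or volume reduction), not for a balanced split. Report the other components separately, and state the expected number of failures with the resulting precision. On the quoted TLVR rate that is still only about 3 in 20 (20 × 0.16 = 3.2), which is why the continuous analysis should carry the weight.

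The cost is wording in Sections 3, 6, 8.1 and 11.2 and a little more analysis. The downside is that some patients who benefit on another measure count as non-responders in the binary contrast; the separate component reports will show them. The definition governs analysis only and leaves patient care unchanged. It should be settled before outcomes are known.
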